| IEC | Independent Ethics Committee |
| IGF-1 | Insulin-like Growth Factor-1 |
| ILAE | International League Against Epilepsy |
| IMP | Investigational Medicinal Product |
| IND | Investigational New Drug |
| ICAB | International Cardiology Advisory Board |

ZX008 (Fenfluramine Hydrochloride)**ZX008-1601 Clinical Study PA 4.0 (Japan) 25 July 2022**

| ABBREVIATION | DEFINITION |
|---------------------|---|
| IRB | Institutional Review Board |
| IU | International Unit |
| IWR | Interactive Web Response (System) |
| KD | Ketogenic diet |
| kg | Kilogram |
| Leiter-3 | Leiter International Performance Scale-Revised |
| LGS | Lennox-Gastaut syndrome |
| LH | Luteinizing Hormone |
| M | Maintenance period |
| MCDS | Mean change in number of seizures that results in drops |
| MCSF | Mean Convulsive Seizure Frequency |
| MedDRA | Medical Dictionary for Regulatory Activities |
| mg | Milligram |
| mg/kg/day | Milligram per kilogram per day |
| Min | Minutes |
| mITT | Modified Intent-to-Treat |
| mL | Milliliter |
| MS | Myoclonic seizure |
| OLE | Open-label extension |
| PopPK model | Population Pharmacokinetic model |
| PK | Pharmacokinetics |
| PP | Per Protocol |
| QoL | Quality of Life |
| QOLCE | Quality of Life in Childhood Epilepsy |
| QTcF | corrected QT interval using Fredericia method |
| SAE | Serious Adverse Event |
| SAF | safety population |
| SAP | Statistical Analysis Plan |
| SD | Standard Deviation |
| SE | Status epilepticus |
| SMEI | Severe Myoclonic Epilepsy Of Infancy |
| STP | Stiripentol |
| SUDEP | Sudden Unexpected Death in Epilepsy |
| T+M | Titration plus Maintenance Periods |
| t _{1/2} | Terminal half-life |
| TA | Tonic/atonic seizure |
| THC | Tetrahydrocannabinol |
| T _{max} | Time to maximum concentration |
| TS | Tonic seizure |
| TSH | Thyroid Stimulating Hormone |
| ULN | Upper Limit of Normal |
| USA | United States of America |
| USP | United States Pharmacopeia |
| VABS | Vineland Adaptive Behavior Scale |
| VNS | Vagal Nerve Stimulator/Stimulation |
| ZX008 | Fenfluramine Hydrochloride Oral Solution |

ZX008 (Fenfluramine Hydrochloride)
ZX008-1601 Clinical Study PA 4.0 (Japan) 25 July 2022

STUDY SYNOPSIS

| | |
|--|--|
| Study Title: A Two-Part Study of ZX008 in Children and Adults with Lennox-Gastaut Syndrome (LGS); Part 1: A Randomized, Double-blind, Placebo-controlled Trial of Two Fixed Doses of ZX008 (Fenfluramine Hydrochloride) Oral Solution as Adjunctive Therapy for Seizures in Children and Adults with LGS, Followed by Part 2: An Open-label Extension to Assess Long-Term Safety of ZX008 in Children and Adults with LGS | |
| Study Number: ZX008-1601 | |
| Study Product: Fenfluramine Hydrochloride Oral Solution, ZX008 | |
| Type of Study: Part 1: Efficacy and safety study Part 2: Long-term safety study | Indication Studied: Adjunctive therapy for seizures in Lennox-Gastaut syndrome (LGS) |
| Phase of Development: Phase III | Countries: North America, Europe, Japan, and Australia |
| Sponsor: Zogenix International Limited | |
| Coordinating Investigator: [REDACTED] | |
| Estimated Duration of Individual Subject Participation: The duration of participation in the study for an individual subject in the double-blind study (Part 1) is expected to be up to 20 weeks. The duration of participation in the open-label extension (Part 2) is up to 72 months or until ZX008 is approved in a subject's country of residence and listed on a patient's health plan formulary, whichever occurs first. The total participation time is up to approximately 77 months. Regardless of whether subjects end participation early, do not continue with the open-label extension, or roll over to the open-label extension, all subjects who do not transition to commercial drug will have a follow-up visit 3 to 6 months after the last dose of study medication for final safety monitoring. | |
| Objectives: The primary objective of Part 1 is the primary objective of the entire study. Part 1 The primary objective of Part 1 is: 
 To evaluate the effect of ZX008 0.8 mg/kg/day versus placebo as adjunctive therapy for the treatment of uncontrolled seizures in children and adults with Lennox-Gastaut syndrome (LGS) based on the change in frequency of seizures that result in drops between baseline and the combined Titration and Maintenance Periods (T+M) The key secondary objectives of Part 1 are: 
 To evaluate the effect of ZX008 0.2 mg/kg/day versus placebo as adjunctive therapy for the treatment of uncontrolled seizures in children and adults with LGS based on the change in frequency of seizures that result in drops between baseline and T+M To evaluate the effect of ZX008 0.2 and 0.8 mg/kg/day (independently) versus placebo on the proportion of subjects who achieve a $\geq 50\%$ reduction from baseline in the frequency of seizures that result in drops To evaluate the effect of ZX008 0.2 and 0.8 mg/kg/day (independently) versus placebo on the Clinical Global Impression – Improvement rating, as assessed by the Principal Investigator See Statistical Methods (Section 10.1.5.1) for hierarchical testing procedure. | |

ZX008 (Fenfluramine Hydrochloride)

ZX008-1601 Clinical Study PA 4.0 (Japan) 25 July 2022

Additional secondary efficacy objectives of Part 1 are:

- To evaluate the effect of ZX008 0.2 and 0.8 mg/kg/day (independently) versus placebo on the following endpoints:
 - Change in the frequency of all countable motor seizures between baseline and T+M (countable seizures include: generalized tonic-clonic seizures [GTC], tonic seizures [TS], clonic seizures [CS], atonic seizures [AS], tonic/atonic seizures [TA], clearly recognizable focal seizures [FS], and myoclonic seizures [MS] that result in a drop)
 - Change in the frequency of all countable seizures (ie, motor and non-motor) between baseline and T+M
 - Change in frequency of seizures that result in drops between baseline and the Maintenance Period (M)
 - Change in the frequency of countable motor seizures that do not result in drops between baseline and M
 - The proportion of subjects who achieve a worsening or no change (i.e $\leq 0\%$ reduction), $>0\%$, $\geq 25\%$, $\geq 50\%$, $\geq 75\%$, 100% reduction, and “near seizure freedom” (ie, 0 or 1 seizures) between baseline and T+M, and baseline and M, in all countable motor seizures (GTC, TS, AS, TA, FS, MS with a drop); in countable motor seizures that do not result in drops; and in all seizures that result in drops
 - Number of seizure-free days, defined as 1) days with no countable seizures and 2) days with no seizures that result in drops
 - Longest interval between seizures that result in drops
- To evaluate the effect of ZX008 0.2 and 0.8 mg/kg/day (independently) versus placebo on the following endpoints:
 - Clinical Global Impression – Improvement rating, as assessed by the parent/caregiver

The safety objectives of Part 1 are:

- To evaluate the safety and tolerability of ZX008 0.2 and 0.8 mg/kg/day versus placebo with regard to adverse events (AEs), laboratory parameters, physical examination, neurological examination, vital signs (blood pressure, heart rate, temperature, and respiratory rate), electrocardiograms (ECG), echocardiograms (ECHO), body weight, and BMI
- To evaluate the change from baseline in cognition using age-appropriate Behavior Rating Inventory of Executive Function (BRIEF)

The pharmacokinetic (PK) objective of Part 1 is:

- To evaluate the PK of ZX008 0.2 and 0.8 mg/kg/day at steady state in subjects <18 years and ≥ 18 years with LGS using a non-compartmental analysis; and obtain exposure data that will be used in population pharmacokinetic (PopPK) analysis, the results of which will be reported separately..

The exploratory objectives of Part 1 are:

- To compare the ZX008 0.2 and 0.8 mg/kg/day doses on primary, secondary and safety endpoints
- To evaluate the effect of ZX008 0.2 and 0.8 mg/kg/day (independently) versus placebo on the following endpoints:
 - The frequency of rescue medication usage
 - The incidence of medical services used to treat seizures
 - The incidence of status epilepticus
 - The change from baseline in behavior using the Vineland Adaptive Behavior Scale (VABS) (Cohort A)
 - The change from baseline in QoL using the Quality of Life in Childhood Epilepsy (QOLCE) Assessment
 - The change from baseline in caregiver burden using the Zarit Caregiver Burden Inventory
 - The change from baseline in affective symptoms of the parent/caregiver using the Hospital Anxiety and Depression Scale (HADS)

ZX008 (Fenfluramine Hydrochloride)
ZX008-1601 Clinical Study PA 4.0 (Japan) 25 July 2022

Part 2

The primary objective of Part 2 is:

- To assess the long-term safety and tolerability of ZX008 in children and adults with LGS with regard to adverse events (AEs), laboratory parameters, physical examination, neurological examination, suicidality, cognition (BRIEF), vital signs (blood pressure, heart rate, temperature, and respiratory rate), electrocardiograms (ECG), echocardiograms (ECHO), body weight, and BMI.

The secondary objectives of Part 2 are:

- To assess the effect of ZX008 relative to the baseline on the following effectiveness measures:
 - The change in the frequency of seizures that result in drops
 - The change in the frequency of all countable motor seizures (GTC, TS, CS, AS, TA, FS, MS with a drop)
 - The change in the frequency of all countable seizures
 - The proportion of subjects who achieve a worsening or no change (ie, $\leq 0\%$ reduction), $>0\%$, $\geq 25\%$, $\geq 50\%$, $\geq 75\%$, 100% reduction, and “near seizure freedom” (ie 0 or 1 seizures) in frequency of all countable seizures that result in drops, countable motor seizures that do not result in drops, all countable motor seizures, all countable seizures, and all countable seizures that do not result in drops
 - Number of seizure-free days, defined as 1) days with no countable seizures and 2) days with no seizures that result in drops
 - Longest interval between seizures that result in drops
- To evaluate the effect of ZX008 on the following endpoints:
 - Clinical Global Impression – Improvement rating, as assessed by the Principal Investigator
 - Clinical Global Impression – Improvement rating, as assessed by the parent/caregiver

The exploratory objectives of Part 2 are:

- To determine the incidence of the following on subjects receiving ZX008:
 - The incidence of medical services used to treat seizures
 - The incidence of status epilepticus
 - The use of rescue medication
- To assess the effect of ZX008 on the following measures:
 - The change from baseline in QoL using the QOLCE
 - The change from baseline in caregiver burden using the Zarit Caregiver Burden Inventory
 - The change from baseline in affective symptoms of the parent/caregiver using the Hospital Anxiety and Depression Scale (HADS)

Methodology:

This is an international multicenter study being conducted in two parts. Up to approximately 80 study sites in North America, Europe, Japan, and Australia are initially planned to participate. Part 1 is a double-blind, parallel-group, placebo-controlled, study to assess the efficacy and safety of two doses of ZX008 when used as adjunctive therapy for seizures in children and adult subjects with LGS. The study will include 2 cohorts: Cohort A will include randomized subjects from North America, Europe,

ZX008 (Fenfluramine Hydrochloride)**ZX008-1601 Clinical Study PA 4.0 (Japan) 25 July 2022**

and Australia; Cohort B will include randomized subjects from Japan only. The primary study endpoint is assessed from Part 1 Cohort A data. The primary analysis will be conducted when the last subject in Cohort A has completed Part 1. Cohort B will be analyzed independently with an interim analysis occurring after the last subject in Cohort B completes 12 months in Part 2 and a final analysis when the last subject in Cohort B completes Part 2. Part 2 will be an open-label, flexible-dose extension for subjects completing Part 1 of the study.

Part 1 will consist of a 4-week baseline, 2-week titration, 12-week maintenance, and 2-week taper or transition period. The 4-week Baseline Period will consist of the establishment of initial eligibility during a screening visit to include an assessment of cardiac parameters (ECG and ECHO), followed by an observation period where subjects will be assessed for baseline seizure frequency based on recordings of daily seizure activity entered into a diary. Upon completion of the Baseline Period, subjects who qualify for the study will be randomized (1:1:1) in a double-blind manner to receive 1 of 2 doses of ZX008 (0.2 mg/kg/day, 0.8 mg/kg/day; maximum dose: 30 mg/day [or 0.5 mg/kg/day, maximum 20 mg/day, for subjects taking concomitant stiripentol (STP)]) or placebo. Randomization will be stratified by weight (<37.5 kilograms [kg], ≥37.5 kg) to ensure balance across treatment arms, and at least 25% of subjects will be in each weight group. All subjects will be titrated to their blinded randomized dose over a 2-week Titration Period. Following titration, subjects will continue treatment at their randomly assigned dose over a 12-week Maintenance Period. Total treatment time from the beginning of the Titration Period through the end of the Maintenance Period is 14 weeks. Subjects will have ECG and ECHO assessments at weeks 6 and 14 during the Maintenance Period. At the end of the Maintenance Period (or early discontinuation), all subjects will undergo a blinded 2-week taper or transition period (Post-Dosing Follow-Up) depending on whether they exit the study or are enrolled in Part 2, the long-term open-label extension, respectively. A follow-up ECG and ECHO will be performed 3-6 months after study drug discontinuation for early termination, or for those subjects who complete the study but do not enter the open-label extension part. If there are any findings at the 3-month post-dose follow-up, a second follow-up will be repeated at 6 months and then every 3 months until resolved or stabilized.

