In an integrated analysis of safety of the double-blind studies, 117 (95.9%) subjects in any ZX008 treatment group and 68 (81.0%) subjects in the combined placebo group reported at least 1 TEAE. The most common ($\geq 10\%$) TEAEs reported in subjects receiving any dose of ZX008 were: blood glucose decreased, constipation, decreased appetite, diarrhea, echocardiogram abnormal, fall, fatigue, lethargy, nasopharyngitis, pyrexia, seizure, somnolence, status epilepticus, tremor, upper respiratory tract infection, vomiting, and weight decreased. All of the echocardiogram abnormal TEAEs were trace mitral or trace aortic valve regurgitation, which are normal physiological findings seen in healthy children ([Webb 2015](#)). A total of 15 (12.3%) subjects in any ZX008 treatment group and 11 (13.1%) subjects in the combined placebo group reported at least 1 serious TEAE. The most frequently reported ($\geq 5\%$) serious AEs (SAEs) were status epilepticus and seizure. A total of 76 (62.3%) subjects in any ZX008 treatment group and 22 (26.2%) subjects in the combined placebo group reported a TEAE determined by the Investigators to be related to the study drug, and 3 (2.5%) subjects in any ZX008 treatment group and 1 (1.2%) subject in the combined placebo group reported a serious TEAE determined to be related to the study drug. During the double-blind treatment periods, 7 (5.7%) subjects in any ZX008 treatment group and 1 (1.2%) subject in the combined placebo group reported a TEAE that lead to discontinuation from study participation. There were no deaths during the double-blind treatment periods.

Subjects in Study 1 and Study 1504 if eligible could participate in Study 1503, an open-label long-term, safety extension study that is currently ongoing. All subjects in Study 1503 started ZX008 at 0.2 mg/kg/day and could flexibly titrate to a maximum dose of 0.8 mg/kg/day, maximum 30 mg/day (if not receiving a concomitant STP regimen) or 0.5 mg/kg/day, maximum 20 mg/day (if receiving concomitant STP regimen), based on effectiveness, safety and tolerability. Though primarily a safety study, subjects in Study 1503 maintained a daily seizure diary and continued to complete rating scales on overall effectiveness and quality of life measures.

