In the event that the study is terminated prematurely then the procedure for termination should be followed as described in [Section 3.7](#). Concern for the interests of the subject will always prevail over the interests of the study.

The reason for, and date of discontinuation from participation in the study must be recorded in detail in the eCRF and in the subject's medical records (eg, AEs, lack of compliance, lost to follow-up, etc). If possible, the subject/subject's legally authorized representative should confirm his decision in writing.

The investigator will attempt to complete all procedures usually required at the end of the study at the time when the subject's participation in the study is discontinued or as close as possible to that time. Specific procedures required for each Part of the study are described in [Section 6.1.2.9](#) and [Section 6.2.4](#). As far as possible, a complete final examination must be performed on all subjects who do not complete the study according to the study protocol.

Data collected until the time a subject discontinues participation in the study will be handled in the same manner as data for subjects completing the study. Where possible, further information will be collected if any AEs are experienced by a subject after discontinuing participation in the study.

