10.1.1 DETERMINATION OF SAMPLE SIZE

The sample size for Part 1 Cohort A was estimated under the assumption that adding ZX008 at 0.8 mg/kg/day to current therapy will lead to a mean decrease in drop seizures that is 30 percentage points greater than adding placebo to current therapy. For example, if adding placebo leads to a 10% decrease in seizures, then adding the high dose of ZX008 would be expected to decrease seizures by at least 40%.

The variability expected in the trial was estimated from a Phase 3 trial of clobazam for patients with Lennox-Gastaut syndrome (Ng 2011) leading to an assumption that the SD is 50%. Other assumptions include an allowance for 20% dropouts between randomization and the start of the maintenance period.

Under these assumptions, and using a Wilcoxon rank-sum test to approximate the primary comparison between the ZX008 0.8 mg/kg/day and placebo groups, a sample size of 63 subjects per treatment group affords 90% power to detect a difference between groups that is significant at the $\alpha=0.05$ level. Assuming a 20% drop-out rate prior to the start of the maintenance period yields a requirement for an additional 16 subjects per group for a total of 79 subjects per treatment group. Similar calculations for the 0.2 mg/kg/day ZX008 group lead to a total required sample size of 237. The number of subjects randomized into Part 1 Cohort A is estimated to be approximately 250 due to the long baseline period.

The sample size of 10 to 15 subjects per treatment group in Cohort B is expected to provide a descriptive assessment of whether the treatment effect in Japanese subjects is similar that observed in Cohort A subjects from the rest of the world.

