10.1.2.2 Modified Intent-to-Treat (mITT) Population

The mITT Population is defined as all randomized subjects who receive at least one dose of ZX008 or placebo and for whom at least one week of diary data are available. Subjects will be analyzed according to the treatment group to which they were randomized. The primary comparison of ZX008 0.8 mg/kg/day to placebo, who complete at least 4 weeks of diary data in the maintenance period, as well as key secondary analyses, will be performed on the mITT Population.

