10.1.6.1 Efficacy Analyses

Primary Efficacy Analysis

The primary efficacy endpoint for Part 1 is the percent change in frequency of seizures that result in drops (DSF: drop seizure frequency) per 28 days between the combined Titration and Maintenance (T+M) and Baseline periods in Cohort A. The DSF will be calculated from all available data collected during the Baseline and T+M Periods without imputation. The percent change from baseline DSF will be calculated as the the change in DSF between T+M and Baseline / DSF during Baseline \times 100. Both the mean and median percent change in DSF Both the mean and median percent change in DSF will be presented.

The primary endpoint will be assessed using a nonparametric, rank analysis of covariance (ANCOVA) with treatment group (ZX008 0.8 mg/kg/day, ZX008 0.2 mg/kg/day or placebo) and weight group (<37.5 kg, \geq 37.5 kg) as factors; rank baseline DSF as a covariate; and rank percent change in DSF from baseline as the response variable. The primary analysis will compare the ZX008 0.8 mg/kg/day group to the placebo group at the $\alpha=0.05$ level of significance. The difference between the ZX008 0.8 mg/kg/day group and the placebo group in percent change in DSF, and its 95% confidence interval, will be estimated using the Hodges-Lehmann method.

As a sensitivity analysis, the primary endpoint will also be analyzed using a parametric ANCOVA that incorporates treatment group and weight group as factors; log baseline DSF as a covariate; and log DSF during T+M as the response variable. Significance will be assessed by a model contrast that compares the ZX008 0.8 mg/kg/day group to the placebo group. The size of the treatment effect will be estimated by exponentiating the difference between the ZX008 0.8 mg/kg/day group and the placebo group derived from the model. Another sensitivity analysis will compare the ZX008 0.8 mg/kg/day group to the placebo group using a Wilcoxon rank-sum test.

Key Secondary Analyses

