The first key secondary endpoint for the ZX008 0.8 mg/kg/day group – the proportion of subjects who achieve a \geq 50% reduction from baseline in the frequency of seizures that result in drops – is derived directly from the primary endpoint, but is widely considered a benchmark for clinical meaningfulness of a medical intervention for seizures. The comparison will be made using a logistic regression model that incorporates the same factors and covariate as the ANCOVA used in the primary analysis. The second key secondary endpoint – the proportion of

ZX008 (Fenfluramine Hydrochloride)
ZX008-1601 Clinical Study PA 4.0 (Japan) 25 July 2022

subjects assessed by the Investigator as minimally, much, or very much improved on the CGI-I will be analyzed using a Cochran-Mantel-Haenszel test (CMH) stratified by weight strata.

The percent change from baseline DSF in the ZX008 0.2 mg/kg/day group will be compared to the placebo group using the same methods employed for the primary analysis. In particular, the same ANCOVA model will be used. Nonparametric methods will be used if normality assumptions do not hold. Analyses of other key secondary endpoints involving the ZX008 0.2 mg/kg/day group will employ similar methods as those used to compare ZX008 0.8 mg/kg/day to placebo.

Multiplicity Strategy and Testing Hierarchy

The efficacy analyses will employ a serial gatekeeper strategy to maintain the Type 1 error rate at $\alpha=0.05$ across the family of analyses that support the primary and key secondary objectives. The strategy specifies a hierarchy of significance tests where each test acts as a gatekeeper to the tests below it.

The hierarchy starts with the primary analysis comparing ZX008 0.8 mg/kg/day to placebo on the percent change from baseline in DSF. The next two steps in the hierarchy also entail comparisons of ZX008 0.8 mg/kg/day to placebo on two key secondary endpoints. The last three steps in the hierarchy all involve comparisons of ZX008 0.2 mg/kg/day to placebo.

Below is a complete list of steps in the testing hierarchy in order:

1. Compare ZX008 0.8 mg/kg/day to placebo on the percent change in DSF from baseline in DSF.
2. Compare ZX008 0.8 mg/kg/day to placebo on the proportion of subjects who achieve a $\geq 50\%$ reduction from baseline in DSF.
3. Compare ZX008 0.8 mg/kg/day to placebo on the change from baseline in the number of all countable motor seizures.

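### Near seizure freedom is an unscaled count of 0 or 1 seizures with no minimum observation time, so an early dropout can be scored near seizure-free or 100% reduced by chance

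*Protocol*

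**What the plan says.** The Synopsis (Part 1 additional secondary objectives and endpoints) and Section 2.1.3 list response categories that end with 100% reduction and near seizure freedom. The latter is given as "ie, 0 or 1 seizures) between baseline and T+M, and baseline and M". It is a number of seizures, not a rate, and no diary length is attached.

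Four other statements govern how a short diary is used:

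- Section 10.1.6.1, on drop seizure frequency (DSF): "The DSF will be calculated from all available data collected during the Baseline and T+M Periods without imputation".
- Section 4.5, on subjects who stop: "Data collected until the time a subject discontinues participation in the study will be handled in the same manner as data for subjects completing".
- Section 10.1.2.2 defines the mITT set as randomized, dosed subjects "for whom at least one week of diary data are available". It does not say that this week must follow randomization. The same section then describes the primary comparison as made in subjects "who complete at least 4 weeks of diary data in the maintenance period", and names the key secondary analyses in that sentence.
- Section 10.1.6.1 says of the ≥50% responder endpoint that it "is derived directly from the primary endpoint", so it inherits the available-data rule. It is tested at steps 2 and 5 of the hierarchy.

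No section classes an early dropout as not having achieved a response category.

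**The concern.** A fixed count is easier to stay under when the subject is watched for less time. Under Section 10.1.5, T+M runs over Study Days 1 to 99 and M over Days 16 to 99. A completer must therefore have at most one seizure in 99 days (or 84 for M) to be called near seizure-free, while a subject who leaves on Day 8 needs at most one in 8 days. The same holds for 100% reduction, which a short diary without events satisfies. Successes of this kind carry no information about the drug, and they would sit in the same table rows as genuine near-freedom over 14 weeks.

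A second weakness needs no dropout. Near-freedom is also scored for motor seizures that do not cause drops, but entry (Sections 4.1.1 and 4.2) sets a minimum frequency for drop seizures only. A subject with 0 or 1 non-drop motor seizures at baseline can meet the definition without improving.

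**Working it through.** **The plan's dropout figure.** Section 10.1.1: "Assuming a 20% drop-out rate prior to the start of the maintenance period", 63 / (1 − 0.20) = 78.75, so 79 per group, 16 more than 63, and 3 × 79 = 237. This reproduces. The 63 is also sound: a two-sample t calculation for a 30-point difference and SD 50 gives 59.35, and 59.35 × π/3 = 62.15, so 63.

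**Inputs from the protocol.** Entry floor of 2 drop seizures per week, that is 8 per 28 days (Section 4.2); T+M of 99 days (Section 10.1.5); mITT minimum of 7 diary days (Section 10.1.2.2).

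**Assumptions.** Counts are Poisson and the on-study rate equals the baseline rate (no drug effect). Negative binomial counts with dispersion 0.5 serve as a check.

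**Formula.** With baseline b per 28 days and d diary days, μ = b × d/28, P(0) = e^(−μ) and P(0 or 1) = e^(−μ)(1 + μ).

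At the floor, b = 8:

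| Diary days | μ | P(0 or 1) | P(0), i.e. 100% reduction |
|---|---|---|---|
| 7 | 2.00 | 40.6% | 13.5% |
| 8 | 2.29 | 33.4% | 10.2% |
| 14 | 4.00 | 9.2% | 1.8% |
| 99 | 28.3 | 1.5 × 10⁻¹¹ | practically 0 |

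With negative binomial counts, P(0 or 1) is 50% at 7 days, 26% at 14 and 1.3% at 99.

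**Dependence on baseline.** With 7 days of diary, Poisson P(0 or 1) is 40.6% at 2 per week, 19.9% at 3, 4.0% at 5 and 0.05% at 10.

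**Maintenance version.** A subject who leaves on Day 20 has M data for Days 16 to 20, 5 days. μ = 8 × 5/28 = 1.43 and P(0 or 1) = 58%. A subject who leaves before Day 16 has no M data, and the protocol does not say whether that subject stays in the denominator.

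**Per-arm rate.** Averaging P(0 or 1) over last diary days 7 to 15 gives 20.4% at baseline 8, 7.3% at 12 and 1.0% at 20. If the planned 20% all left in that window, each arm would gain 4.1, 1.5 or 0.2 percentage points of chance near-freedom (negative binomial: 7.0, 4.5, 2.3).

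**Between-arm difference.** The only arm-specific withdrawal figures are in Section 1.3: "7 (5.7%) subjects in any ZX008 treatment group and 1 (1.2%) subject in the combined placebo group reported a TEAE that lead to discontinuation". The gap is 5.7 − 1.2 = 4.5 points. If all of it fell evenly over Days 7 to 15:

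- baseline 8: 4.5 × 0.204 = 0.9 points
- baseline 12: 4.5 × 0.073 = 0.3 points
- baseline 20: 4.5 × 0.0098 = 0.04 points

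The negative binomial check gives 4.5 × 0.350 = 1.6 points at baseline 8. The same Poisson exercise for ≥50% reduction gives 1.1, 0.6 and 0.3 points, if early dropouts enter that analysis at all.

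**The case against.** A reader might infer that the rule favours the drug by several points and threatens the gated ≥50% tests. The documents do not support that.

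- The 20% is a planning allowance applied alike to every group. Equal losses raise all arms together and largely cancel.
- The 5.7% and 1.2% come from Dravet studies pooled over 14 to 15 weeks, not from the first two weeks in this disease. Putting the whole gap into Days 7 to 15 is already generous.
- Direction is open. Section 4.5 also lists withdrawal for worsening seizures, which may be commoner on placebo. High-dose subjects reach target dose only on Day 9, so their early diary reflects mostly lower doses.
- Near seizure freedom is an additional secondary endpoint, outside the six-step hierarchy.
- If the four-week clause in Section 10.1.2.2 is the working rule, early dropouts may never enter steps 2 and 5.
- The only LGS frequency in the protocol, a mean of 60 major motor seizures per month in the pilot study (not drop seizures), would make chance near-freedom negligible under Poisson.
- Early leavers keep a diary through taper, and seizures are reviewed 14 days after stopping. If those days counted, a Day 8 leaver would have up to about 22 days and P(0 or 1) at the floor would be 1.4%. The protocol does not say whether they count.

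These points limit size, direction and reach, and they stand. They do not remove the defect in the definition. It is also not a matter merely left to the SAP: the protocol itself fixes the count, the available-data rule, the equal handling of dropouts and the one-week minimum. The four-week clause does not mention near seizure freedom and, if it applied, would exclude dropouts rather than count them as not achieved.

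**Conclusion.** The concern holds for near seizure freedom and 100% reduction over T+M, and over M for subjects who leave soon after Day 15. Followed literally, the protocol gives a no-effect subject at the entry floor a 41% chance of the near-freedom label with 7 diary days, against practically none over the full period. This is material near 2 to 3 drop seizures per week and fades quickly above that. As a bias between arms it is small under Poisson, about 0.9 points or less on the assumptions shown, and its direction is not established. For the ≥50% key secondary endpoint the problem is narrower: whether early dropouts enter steps 2 and 5 depends on two diary clauses that conflict. The figures rest on Poisson counts, an unchanged seizure rate and a diary that ends at discontinuation; overdispersion raises them. The sample size is unaffected.

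**What to change.** 1. For 100% reduction and near seizure freedom, count the outcome as achieved only if the subject completed the period concerned (T+M or M) with diary data. Keep all other mITT subjects in the denominator as not achieved.
2. Reconcile the one-week and four-week diary clauses in Section 10.1.2.2, and state which subjects enter the key secondary analyses.
3. For the ≥50% key secondary endpoint, add a sensitivity analysis that scores early discontinuations as non-responders. Making this the main rule is a debatable choice and is not needed here.
4. For near-freedom in seizure classes without drops, restrict the analysis to subjects with more than 1 such seizure at baseline.

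The cost is wording and one added sensitivity analysis, with no extra subjects, visits or data. Reported rates will be slightly lower, most of all in the arm with more early dropouts.
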